Concomitant Medications		Conti	nuous from si	gning ICF until 30 days after last dose of study therapy		
Subsequent Anticancer Therapy					X	x
AESI, irAEs and SAEs	Continuous from signing ICF until 90 days after last dose of study therapy or resolution/stabilization					
Hematology 3,4	Х	C1D1	C2D1	C3D1 then Q6W (ie, at every other visit) and as clinically indicated	Х	
Chemistry ^{3,4}	Х	C1D1	C2D1	C3D1 then Q6W (ie, at every other visit) and as clinically indicated	Х	
INR, PT, PTT (or aPTT)	Х	As clinically indicated				
Thyroid Monitoring 3,5	Х	Q6W (±7D) and as clinically indicated				
Pregnancy Test ^{3,6}	≤2D before C1D1	Q12W (±14D)				

Confidential Page 20 of 109

Cutaneous, Subcutaneous and Nodal Lesion Measurement and Photographs ^{3,7}	Х	C1D1, C1D8, C1D15	C2D1, C2D8, C2D15	Day 1 of each Cycle	х	per SOC
Tumor Imaging ⁸	≤6W before C1D1	6 & 12W after C1D1, then Q12W thereafter. Crossover participants must have re-baseline imaging within 28D prior to administration of crossover C1D1 (i.e. first dose of anti-PD-1 therapy)				
Tissue Biopsy ⁹ All samples to be collected prior to dosing at the given timepoint	Prior to PV Immunization Booster	C1D8	C2D1	At the time of PD ± 1 week (per RECIST) Crossover Only: within 1 week prior to crossover C1D1, 1 week after crossover C1D1 (pre-dose, if applicable), 3 weeks (+7d; pre-dose) after crossover C1D1, and at the time of PD ± 1 week (per RECIST) on the crossover regimen		
Blood Collection ¹⁰ All samples to be collected prior to dosing at the given timepoint	Prior to PV Immunization Booster	C1D1, C1D8	C2D1	C3D1 and at the time of PD ± 1 week (per RECIST) Crossover Only: within 1 week prior to crossover C1D1, 1 week after crossover C1D1 (pre-dose, if applicable), 3 weeks (+7d; pre-dose) after crossover C1D1, and at the time of PD ± 1 week (per RECIST) on the crossover regimen		
Lerapolturev Administration ¹²		C1D1, C1D8, C1D15	C2D1, C2D8, C2D15	C3D1 and Q3W thereafter		
ARM 2: Anti-PD-1 Administration (pembrolizumab)		C1D1	C2D1 (if given Q3W)	C3D1 and Q3W or Q6W thereafter per pembrolizumab package insert		
Crossover from Arm 1 to Arm 2 13		If participant meets protocol-defined criteria				
Lerapolturev Shedding: Injected Lesion ¹⁴		C1D1 (post- injection), C1D4, C1D8, C1D15 (post- injection), C1D18	C2D1, C2D15 (post- injection), C2D18	C3D1		
Lerapolturev Shedding: Stool			C2D8 (±3D)			

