6.3 Participant Withdrawal from the Trial

Participants may be withdrawn from the study under any of the following circumstances:

- Withdrawal of consent
- Lost to follow-up
- Administrative reasons (eg, Sponsor decision)
- Major violation of the protocol
- If in the opinion of the investigator, it is in the best interest of the participant
- Non-compliance
- Termination of the study

Participant follow-up should continue as specified in the protocol until the scheduled date of study completion, or until recovery or stabilization of an AE, whichever comes last. All

Confidential Page 71 of 109

participants that permanently discontinue study treatment should be followed for survival and disease progression outcomes; these assessments may be made via telephone contact if local follow-up is not possible. At minimum, all participants should have an EOT visit that includes tumor measurements (imaging and cutaneous measurements) and a focused physical assessment prior to study withdrawal. Chemistry and hematology should be collected, if possible. Investigators should also provide a final and best overall anti-tumor response assessment with the eCRF.

Lost to Follow-up

A participant will be considered lost to follow-up if they fail to return for 2 scheduled visits and are unable to be contacted by the study site. The following actions must be taken if a participant fails to return to the clinic for a required study visit:

- The site must attempt to contact the participant, reschedule the missed visit as soon as possible, counsel the participant on the importance of maintaining the assigned visit schedule, and ascertain whether the participant wishes to and/or should continue in the study.
- Before a participant is deemed lost to follow-up, the investigator or designee
 must make every effort to regain contact with the participant (where possible,
 3 telephone calls and, if necessary, a certified letter to the participant's last
 known mailing address or local equivalent methods). These contact attempts
 should be documented in the participant's medical record.
- Should the participant continue to be unreachable, they will be considered to have withdrawn from the study.

Participants who are lost to follow-up may be replaced at the Sponsor's discretion.

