- 15. End of Treatment Visit should be performed within 28 days after the last dose of study drug(s). The visit should include a focused and symptom directed physical assessment, cutaneous, subcutaneous, and nodal tumor measurements (including photographs), as well as radiographic tumor imaging.
- 16. Survival Follow-up: Scans and cutaneous, subcutaneous, and nodal lesion measurements performed per SOC should still be collected for participants in post-EOT survival follow-up who discontinued study treatments for reasons other than disease progression. The collection of lesion measurement (cutaneous, subcutaneous, and nodal, and scans) performed per standard of care should continue until confirmed progression or the start of the next anti-cancer therapy. Sites should continue to collect post-study therapies and survival status for follow-up duration.

Table 3. Schedule of Assessments for Lerapolturev + Nivolumab

NOTE: Cycle length for lerapolturev + nivolumab is 4 weeks. Lerapolturev is administered weekly during Cycles 1 & 2 and every 4 weeks thereafter on the days indicated in the table below. Refer to the table below for the timing of other study assessments to be completed within each cycle.

	Screening		Treatment			Survival Follow-up ¹⁶		
Study Procedure ³	Period	Cycle 1	Cycle 2	≥ Cycle 3				
	(≤ 28D prior to C1D1)		+4W (+7D)	Q4W (+7D)	≤28D after last treatment			
Informed Consent ¹	X							
Medical History	X							
Physical Exam ^{2,3}	X	C1D1	C2D1	Day 1 of each Cycle	X			
Vital Signs ³	Х	C1D1, C1D8, C1D15 C1D22	C2D1, C2D8, C2D15	Day 1 of each Cycle	×			
ECOG Performance Status ³	X	C1D1	C2D1	Day 1 of each Cycle	X			
PV Immunization Booster ¹	≥1W, but ≤6W before C1D1							
Adverse Events				om signing ICF until 30 days after last dose of study therapy				
Concomitant Medications		Continuous from signing ICF until 30 days after last dose of study therapy						
Subsequent Anticancer Therapy		X						
AESI, irAEs and SAEs		Continuous	from signing IC	CF until 90 days after last dose of study therapy or resolution/stabilization				
Hematology 3,4	X	C1D1	C2D1	C3D1 then Q8W (ie, at every other visit) and as clinically indicated	X			
Chemistry ^{3,4}	X	C1D1	C2D1	C3D1 then Q8W (ie, at every other visit) and as clinically indicated	X			
INR, PT, PTT (or aPTT)	X			As clinically indicated				
Thyroid Monitoring 3,5	X		X	Day 1 of each Cycle	X			
Pregnancy Test ⁶	≤2D before C1D1			Q12W (±14D)				

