Because lerapolturev is an immunotherapeutic administered by intratumoral injection, AESIs fall into 2 categories: (1) AEs related to lerapolturev administration (ie, injection site reaction [ISR]), and (2) AEs related to cytokine release syndrome [CRS] and immune effector cell-associated neurotoxicity syndrome [ICANS], which can occur when the body's immune cells release a bolus of inflammatory cytokines in response to an immunotherapy.

AESIs are collected through 90 days post last dose of study drug.

Immune-Related Adverse Events (irAEs)

Any adverse event affecting an organ system through an autoimmune or inflammatory mechanism, whereby the immune system is acting against normal tissue. The list of terms to identify irAEs is as

follows: (1) high level term (HLT): Colitis (excl infective); (2) HLT: Lower respiratory tract inflammatory and immunologic conditions; (3) HLT: Hepatocellular damage and hepatitis NEC; (4) HLT: Hypothalamic and pituitary disorders NEC; (5) HLT: Adrenal cortical hypofunctions; (6) HLT: Diabetes mellitus (incl subtypes); (7) HLT: Nephritis NEC; (8) HLT: Encephalitis NEC; (9) Preferred term (PT): Toxic epidermal necrolysis; (10) PT: Severe cutaneous adverse reaction; (11) PT: SJS-TEN overlap; (12) PT: Stevens-Johnson syndrome. Recommendations for study drug management in the event of an irAE are described in Protocol Section 5.5.

irAEs are collected through 90 days post last dose of study drug.

Concomitant Medications

Concomitant medications are those medications taken on or after the initiation of study drugs through 30 days post last dose of study drug. This definition includes medications started prior to initiation of study drugs and continuing concomitantly with study drugs.

Prior Medications

Prior medications are those medications taken and discontinued prior to initiation of study drugs.

Complete Response (CR)

A CR is defined by:

- disappearance of all target lesions AND
- disappearance of all non-target lesions AND
- all lymph nodes must be non-pathological in size (< 10 mm short axis) AND
- no appearance of new unequivocal lesions.

Partial Response (PR)

A PR is defined by:

- \geq 30% decrease in the sum of diameters of target lesions, taking as reference the baseline sum diameters AND
- non-CR / non-PD or not evaluated non-target lesions AND
- no appearance of new unequivocal lesions.

Stable Disease (SD)

Stable disease (SD) is defined by:

- non-PR / non-PD of target lesions AND

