- non-PD or not all evaluated of non-target lesions AND
- no appearance of new unequivocal lesions.

Progressive Disease (PD)

Progressive disease (PD) is defined by:

- \geq 20% increase in the sum of diameters of target lesions, taking as reference the smallest sum on study (this includes the baseline sum if that is the smallest on study) and an absolute increase of at least 5 mm OR
- unequivocal progression of non-target lesions OR
- appearance of one or more new lesions.

Duration of Response (DOR)

DOR is defined as time since a confirmed objective response (CR or PR) is first observed (ie, the scan date when the response originally occurred prior to confirmation) until unequivocal disease

progression (PD) or death, whichever occurs first. Participants will be censored at the date of the last imaging, if there is no date for PD or death.

Objective Response Rate (ORR)

ORR is defined as the proportion of participants achieving confirmed CR or confirmed PR.

Durable Response Rate (DRR)

DRR is defined as the proportion of participants with confirmed CR or confirmed PR lasting ≥ 6 months.

Overall Survival (OS)

OS is defined as time from start of treatment until death from any cause or last follow-up if participant is alive. Participants who are lost to follow-up will be censored at the last date of contact. The primary analysis will include the following subgroups:

- Participants who received lerapolturev monotherapy
- Participants who received lerapolturev + anti-PD-1
- Participants who crossed over from lerapolturev monotherapy to lerapolturev + anti-PD-1 from treatment group assignment until death from any cause or last follow-up, if participant is alive
- Participants who crossed over from lerapolturev monotherapy to lerapolturev + anti-PD-1 from time of crossover until death from any cause or last follow-up if participant is alive

Progression Free Survival (PFS)

PFS is defined as time (number of months) from start of treatment until date of documented radiologic disease progression or death due to any cause, whichever comes first. Participants not meeting this definition will be censored at the date of the last imaging. The primary analysis will include the following subgroups:

- Participants who received lerapolturev monotherapy
- Participants who received lerapolturev + anti-PD-1

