- Participants who crossed over from lerapolturev monotherapy to lerapolturev + anti-PD-1 from treatment group assignment until death from any cause or last imaging, if participant is alive
- Participants who crossed over from lerapolturev monotherapy to lerapolturev + anti-PD-1 from time of crossover until death from any cause or last imaging if participant is alive

Disease Control Rate (DCR)

DCR is defined as the proportion of participants achieving confirmed CR, confirmed PR, or SD as best response.

Disease Control Rate-6 Months (DCR-6mo)

DCR is defined as the proportion of participants achieving confirmed CR for any duration, confirmed PR for any duration, or SD for ≥ 6 months as best response.

Treatment Period

Treatment period is defined as Cycle 1, Day 1 of study to the EOT.

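### Stable disease has no minimum time from baseline, so a non-progressive scan before Week 6 can count as disease control and DCR can be overstated

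*SAP*

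**What the plan says.** - **DCR.** SAP 3.2.6: "DCR is defined as the proportion of participants achieving confirmed CR, confirmed PR, or SD as best response". No duration is attached to SD.
- **SD.** The same section requires "non-PR / non-PD of target lesions AND" "non-PD or not all evaluated of non-target lesions AND" no new unequivocal lesion. Every element concerns lesions and none concerns time.
- **Best overall response.** SAP 5.6.1.2 refers to Table 4, which has no time condition. A CR or PR followed by NE, NA or PD becomes SD. No row begins with SD.
- **Scheduled imaging.** Protocol Tables 1 and 2: "6 & 12W after C1D1, then Q12W thereafter".
- **EOT assessment.** Protocol 6.3: "At minimum, all participants should have an EOT visit that includes tumor measurements (imaging and cutaneous measurements", together with a best overall response entered by the investigator. Footnote 15 of the SAP schedules lists "cutaneous, subcutaneous, and nodal tumor measurements (including photographs), as well as radiographic tumor imaging" and places the visit within 28 days after the last dose, with no earliest day.
- **Denominator.** SAP 4.2 admits anyone with one injection and one post-baseline assessment, whatever its date.
- **Companion endpoint.** DCR-6mo counts "confirmed PR for any duration, or SD for ≥ 6 months as best response", so it does carry a minimum for SD.

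**The concern.** An unchanged scan two to five weeks after baseline shows mainly that little time has passed. Under the written rules it can still score as disease control. This could happen to a participant who stops for toxicity or clinical decline before the first scheduled scan.

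Nothing else in the plan reliably catches these records. The rule in SAP 5.6.1.1 that makes death or new cancer treatment a failure is written for ORR only. The PD definition in SAP 3.2.6 does not cover clinical deterioration without measured growth.

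DCR is reported with an exact 95% interval by treatment group and schedule. Any upward shift would be largest in the group with the most early stopping. The endpoint may also rest heavily on SD: Protocol 1.2.2.2 reports that stable disease was the best response seen at the December 2021 cutoff.

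**Working it through.** **1. The plan's own figure.** The documents give no target or assumed value for DCR. The nearest figure is for ORR. A Clopper-Pearson interval for 5/15 gives 11.8% to 61.6%, as stated in SAP 3.1. SAP 5.6.2.1 uses the same method for DCR.

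**2. Can an assessment fall before Week 6?** Week 6 is about Day 43. Latest EOT day = last-dose day + 28.

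| Last dose | EOT assessment can fall on |
|---|---|
| Day 1 | Day 1 to 29 |
| Day 8 | Day 8 to 36 |
| Day 15 | Day 15 to 43 |

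Yes. A participant last dosed on Day 8 is assessed before the Week 6 scan in every case. One last dosed on Day 15 is usually assessed before it, but not if the full window is used.

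**3. Effect of one participant.** At n=15 each adds 1/15 = 6.7 points. Take 6 of 15 truly controlled as an illustration:

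| Early SD records | Reported DCR | Exact 95% CI |
|---|---|---|
| 0 | 40.0% | 16.3 to 67.7 |
| 1 | 46.7% | 21.3 to 73.4 |
| 2 | 53.3% | 26.6 to 78.7 |
| 3 | 60.0% | 32.3 to 83.7 |

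**4. Expected excess over a day-36 rule.** Study day 36 is 35 days after Cycle 1 Day 1. The documents give none of the following, so all are assumptions:
- a proportion p stops before Week 6 for reasons unrelated to measured growth;
- stopping time is uniform over 0–42 days and EOT delay is uniform over 0–28 days;
- time to measured PD is exponential with median M;
- there is no later scan.

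Let A be stopping time plus EOT delay. Its density is a/(42×28) for a ≤ 28 and 1/42 for 28 < a ≤ 42. Then

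excess = p × q, where q = ∫₀³⁵ f(a)·2^(−a/M) da.

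With 30.44 days per month:

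| Median PD time | q | p = 5% | p = 10% | p = 20% |
|---|---|---|---|---|
| 1.5 months | 0.356 | 1.8 | 3.6 | 7.1 |
| 2 months | 0.387 | 1.9 | 3.9 | 7.7 |
| 3 months | 0.421 | 2.1 | 4.2 | 8.4 |
| 4 months | 0.439 | 2.2 | 4.4 | 8.8 |

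The last three columns are percentage points. At p = 10% and a median of 3 months, DCR as written is 73.3%. Under the day-36 rule it is 73.3 − 4.2 = 69.1%.

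**5. If later scans exist.** Under the same assumptions P(A < 35) = 0.5, and the chance of no PD by day 42 is 0.727 at a 3-month median. If every early leaver had a standard-of-care scan at about Week 6, the 10% excess would be 10 × (0.421 − 0.5 × 0.727) = 0.6 points. If half did, it would be 10 × (0.421 − 0.5 × 0.5 × 0.727) = 2.4 points.

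**The case against.** Much of the opposing case stands and limits the point.

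- **The EOT measurement is expected, not mandatory.** A reader might infer that every early leaver must have one. Both documents say it should be done, so some will not. Participants with no post-baseline assessment drop out of the efficacy set. That removes a likely failure from the denominator and also tends to raise DCR.
- **Progression is not purely lesion-based.** Protocol 5.4 treats a need for palliative radiotherapy or surgery before progression as progression in the analyses. This closes one route, but not clinical decline without such treatment.
- **Later scans may replace the early one.** Footnote 16 of the schedules asks for standard-of-care scans after EOT from those who stopped for reasons other than progression. Step 5 shows how much this matters.
- **Table 4 does not itself class a lone early assessment as SD.** That class follows from the SD definition, since no row of the table starts with SD.
- **The stopping rates have no source.** The early data in Protocol 1.2.2.2 show no DLTs and no treatment-related Grade ≥3 events in 17 participants, though on the earlier schedule. Eligibility also requires ECOG 0–1 and life expectancy above 12 weeks.

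A reader might also infer that leaving is scored better than staying. Comparing an early leaver's unchanged scan with a 25% increase at Week 6 in someone who stays does not show this, because it mixes growth with timing. A participant who stays and has an unchanged Week 6 scan is also SD. What the documents support is narrower: an earlier look gives less opportunity to observe progression.

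Reporting DCR-6mo alongside helps the reader, but DCR remains a separately named endpoint with its own interval.

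**Conclusion.** The gap is real. Followed as written, the plan lets a non-PD assessment before Week 6 count as disease control when no later scan exists. Relative to a DCR with a minimum SD interval, the error can go only one way, upward or nil.

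The size is 6.7 points per participant at n=15. The expected excess is about 1.8–2.2, 3.6–4.4 or 7.1–8.8 points at 5%, 10% or 20% early stopping, and less where later scans exist. These ranges depend on the assumptions in step 4. The number of early leavers is not in the documents, so they do not show that DCR will in fact be inflated by any given amount.

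The consequence is limited. ORR and the 5-of-15 rule do not use SD, DCR-6mo has its own minimum, and DCR is secondary and descriptive with no threshold attached.

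**What to change.** In SAP 3.2.6 and under Table 4, add:

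- SD counts as best overall response only if documented at or after the first scheduled Week 6 assessment, less a window that the sponsor states. Neither document gives an imaging window. Seven days is one example and would mean at least 35 days.
- The interval runs from Cycle 1 Day 1, or from crossover Day 1 for the crossover analyses. This matters because SAP 3.2.6 counts study day from Cycle 1 Day 1, while Protocol 8.5.4 resets the response baseline at crossover. A rule in study days alone would be met automatically by anyone crossing over after about Week 5.
- If the only post-baseline assessments are earlier and show neither PD nor response, best overall response is NE. These participants stay in the DCR denominator as not controlled.
- A later standard-of-care scan, taken before any new anti-cancer therapy, may satisfy the minimum.

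The cost is a short SAP addition and one date check in the response derivation, with no new data. The downside is that reported DCR may be slightly lower.

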3.3. TIMING OF ANALYSES

The final analysis will be completed after the last participant completes or discontinues the study and the resulting clinical database has been cleaned, quality checked, and locked.

4. ANALYSIS POPULATIONS

Data analyses will be based on the intent-to-treat (ITT), efficacy, safety, and screening analysis sets.

4.1. INTENT-TO-TREAT ANALYSIS SET (ITT)

All participants who sign the ICF and are randomized. The participants in the ITT population will be analyzed based on treatment assigned.

4.2. EFFICACY

Participants receiving at least one lerapolturev injection and at least 1 post-baseline assessment. If a participant crosses over from monotherapy to combination therapy, then the treatment analyzed will be based on the treatment for that participant at the time of the assessment for the efficacy set.

